**PK Subset Study Subjects:**

Those subjects participating in the PK subset will follow the same general schedule with the addition of several overnight stays. Specifically, the PK subset will consist of a screening period (Day -28 to Day -2), 3 check-in and in-house periods (Day -1 to Day 2; Day 13 to Day 14; and Day 27 to Day 31), a dosing complete/ET visit (Day 29), and 2 follow-up telephone calls (Day 42 [+2 days] and Day 58 [+2 days]).

Subjects in the PK subset will check into the clinical investigative site on Day -1, Day 13, and Day 27 and be discharged from the clinical investigative site on Day 2, Day 14, and Day 31. Subjects will check into the clinical investigative site early enough to eat the required meal and then be administered the final dose for that day on Day 13 and Day 27.

When the study drug is not administered at the clinical investigative site, subjects will administer study drug at home.

Serial blood samples for PK analysis of TPOXX will be collected before the first dose of study drug (0 hour) on Days 1, 14, and 28 and up to 24 hours after study drug administration on Day 1 and up to 72 hours after the first dose of study drug on Day 28.

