## **4. STUDY POPULATION**

A total of at least 445 adult male and female subjects will be enrolled at approximately 12 clinical investigative sites in the United States.

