### **Pooling of Sites**

Up to 10 sites in the USA will be used in this study. The PK subset will be enrolled at 1 Phase 1 unit. For the remaining sites, a maximum number of subjects will be agreed upon and enrollment

will be competitive. Thus major differences in subject enrollment numbers per site are not expected, and therefore there will be no inter-subject pooling of data.

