## **Subgroups**

The effects of age group (18 to 30 years, 31 to 45 years, 46 to 64 years, and 65 to 80 years) used for stratification at randomization and site will be investigated for AE and severe AE rates. Time to first AE or severe AE and time to withdrawal for any reason will be calculated.

Study day is relative to first dose of study drug. Study days are calculated with respect to the first dose date as below:

- If the assessment/observation date is on or after the first dose date, then Study Day = Assessment/Observation Date – First Dose Date + 1;
- Otherwise, Study Day = Assessment/Observation Date – First Dose Date.

Baseline will be defined as the last non-missing assessment (including repeated and unscheduled assessments) before the first dose of study drug administration, unless otherwise specified.

For summary of safety assessments, if there are repeated measurements at a time point, the first non-missing assessment at that time point will be used in the summary tables.

Unscheduled results will not be included in the summary tables, except for determining Baseline, but will be presented in data listings.

The methodology and data handling specifications for PK data are detailed in [Section 8](#).

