#### **9.3.1 Time to First Adverse Event**

Time to first AE is defined as the duration from start of the treatment to the first recorded post-dose AE. If the subject does not have an AE, time to first event will be censored at the date of the last adequate assessment; this is expected to be on the Day 42 (+2 day) Follow-up Telephone Call.

Time to First AE (days) = (Date of first AE – Date of first dose) +1

Time to first AE will be analyzed using Kaplan Meier (KM) quartile estimates along with 2 sided 95% CIs. Treatment groups will be compared using the log rank test stratified by age group and clinical investigative site. Statistical significance will be assessed at the 0.5 level. A summary table will be produced.

If a subject does not experience any AE during the study, the time to first AE will be censored at the date of study completion.

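### SAP 9.3.1 prints the log-rank significance level as 0.5 beside 95% CIs, where 0.05 is meant; separately, crossing age group with site costs that test some sensitivity, which a site main effect would mostly recover

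*Combined protocol and SAP*

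**What the plan says.** SAP Section 9.3.1 (Time to First Adverse Event) gives Kaplan-Meier quartiles with 2-sided 95% CIs, then the test: "Treatment groups will be compared using the log rank test stratified by age group and clinical investigative site". The next sentence sets the threshold: "Statistical significance will be assessed at the 0.5 level". SAP 9.3.2 applies the same analysis to time to withdrawal. Protocol 7.3.2 and the synopsis name the same test and the same CIs but state no significance level.

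The SAP does not say how the two factors form strata, and gives no rule for sparse ones. On site numbers, its Pooling of Sites paragraph says "Up to 10 sites in the USA will be used in this study", while Protocol Section 4 says "approximately 12 clinical investigative sites in the United States". Pooling is ruled out: "Thus major differences in subject enrollment numbers per site are not expected, and therefore there will be no inter-subject pooling of data". Protocol 5.3 blocks the 4:1 randomisation within age group and states that site is not a stratification factor.

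SAP 4.5.1 makes the AE rate the primary endpoint and lists the two time-to-event measures among the other endpoints. SAP 9.3 compares the AE rate by a Mantel-Haenszel test stratified by age only.

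**The concern.** There are two matters of different weight.

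First, a 0.5 level cannot be squared with 95% intervals in the same paragraph. Applied as printed, it would label half of all true-null comparisons significant, for both first AE and withdrawal.

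Second, a log-rank test stratified by two factors is normally computed within each age-by-site cell. A cell holding only one arm adds nothing to the comparison. With 89 placebo subjects spread over 40 or more cells, and nothing in the randomisation to balance arms within a site, some cells will have no placebo subject. Even site enrolment, the SAP's reason for not pooling, does not prevent this: the cells are thin when sites are exactly equal. The lost subjects still appear in the Kaplan-Meier estimates, and no count of them is planned. What is at stake is some sensitivity to earlier AEs or withdrawals on TPOXX.

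**Working it through.** **Stated figure.** The documents give no stratum count and no power for this test. Their only probability, in SAP 4.2, reproduces: 1 - 0.99^300 = 0.951, the stated approximately 95%. It does not bear on the log-rank test.

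**Significance level.** A 95% CI corresponds to 1 - 0.95 = 0.05. The printed level is 0.5/0.05 = 10 times that.

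**Strata.** Inputs: 445 subjects, 89 on placebo (SAP 3); 4 age groups; 10 sites (SAP) or 12 (protocol).

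| | 10 sites | 12 sites |
|---|---|---|
| Strata | 4 x 10 = 40 | 4 x 12 = 48 |
| Subjects per stratum | 445/40 = 11.1 | 445/48 = 9.3 |
| Placebo per stratum | 89/40 = 2.2 | 89/48 = 1.9 |
| Chance of no placebo, average stratum | 0.8^11.1 = 0.084 | 0.8^9.3 = 0.126 |
| Expected strata without placebo | 40 x 0.084 = 3.3 | 48 x 0.126 = 6.1 |

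Simulating with equal sites and blocks of 5 within age (block size assumed) gave 3.6 of 40 or 6.6 of 48 one-arm strata, holding 34 or 51 subjects: 34/445 = 7.6%, 51/445 = 11.5%. A second simulation gave about 32 and 52 subjects (7.2% and 11.7%). With moderately unequal sites, about 6 of 40 or 9 of 48 strata had no placebo.

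**Information.** Relative to age-only strata, with no site effect, crossed strata kept 0.818 to 0.915 (a loss of 8-18%) and a site main effect kept 0.962 to 0.976 (a loss of 2-4%). A second simulation with whole-day times put the crossed loss at 15-20%. Hence roughly 10-20%.

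**Power.** The documents give no event rate, hazard ratio (HR) or site variation, so all are assumed: 50% AE rate, HR 1.5, two-sided 0.05, exponential times to Day 42, 4,000 trials per scenario. SDs are on the log-hazard scale; the standard error of a paired difference is 0.4-0.7 points.

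| Scenario | Sites | Crossed log-rank | Cox, site main effect | Gain (points) |
|---|---|---|---|---|
| Site SD 0 | 10 | 66.2% | 71.5% | +5.3 |
| | 12 | 64.4% | 71.2% | +6.8 |
| Site SD 0.5 | 10 | 65.7% | 71.6% | +5.9 |
| | 12 | 63.3% | 71.0% | +7.7 |
| Site SD 0.8 | 10 | 64.2% | 70.7% | +6.5 |
| | 12 | 62.8% | 69.9% | +7.1 |
| Age-by-site SD 0.3 | 10 | 66.3% | 70.5% | +4.2 |
| | 12 | 64.3% | 68.6% | +4.3 |
| Age-by-site SD 0.5 | 10 | 66.4% | 66.8% | +0.4 |
| | 12 | 64.7% | 66.5% | +1.8 |
| Age-by-site SD 0.8 | 10 | 64.3% | 57.9% | -6.4 |
| | 12 | 62.0% | 59.0% | -3.0 |

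Repeat runs at age-by-site SD 0.5 ranged from -1 to about +6 points. At a 10% event rate and HR 2.5, the gain was 2.3 to 4.2 points without age-by-site variation.

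**Phase 1 unit.** SAP: "The PK subset will be enrolled at 1 Phase 1 unit". Its in-house stays could change AE reporting over time. With AE hazards 3 or 5 times higher on visit and in-house days, the gain was still 6-8 points.

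**Type I error.** 4.7-5.7% crossed and 5.1-6.1% Cox. After adjusting for size at site SD 0.5, the gain was 69.2 - 61.8 = 7.4 points (10 sites) and 68.3 - 62.8 = 5.5 (12 sites).

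**The case against.** The planned test is prespecified consistently in protocol and SAP, is valid, and concerns endpoints with no power target. The gain rests on assumed values. On these figures the crossed test is the steadier of the two, at 62-66% power throughout the table, while the Cox test ranges from 58% to 72%. All of this stands, and it is why the change of test is optional.

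Three technical objections also stand and shape the fix.

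- **Ties.** Times are in whole days. With front-loaded onset (an assumption) and site SD 0.5, power was 66.2% crossed, 67.3% Cox-Breslow and 71.6% Cox-Efron at 10 sites, and 63.7%, 66.7% and 71.1% at 12. Breslow gained only 1-3 points here, though 4-7 in another simulation without age-by-site variation. The tie method must be named.
- **Sites without events.** At a 10% event rate, HR 1 and site SD 0.5, at least one site had no events in about 25% (10 sites) or 43% (12 sites) of simulated trials. Such sites add no information to the Cox test either, and should be reported.
- **Route.** SAP Section 11 so far records the dropping of one output, a smaller step than replacing a test named in the protocol.

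A reader might infer more than the documents support:

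- **That the crossed test is invalid.** Its type I error is close to nominal.
- **That the main safety conclusion depends on it.** The primary AE-rate comparison is stratified by age only and is unaffected.
- **That site should be dropped.** At site SD 0.8, age-only power falls to about 55%, below both alternatives. The SAP is also interested in site: age group "used for stratification at randomization and site will be investigated for AE and severe AE rates".
- **That 0.5 was a deliberate choice.** Nothing else in the documents supports it, and the adjacent 95% intervals contradict it.

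**Conclusion.** The printed 0.5 level is wrong as written and needs correcting whatever is decided about strata. It does not strengthen the second point, and the power figures above assume 0.05.

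The crossing of age group with site is a cheap improvement, not an error. The sparsity follows from the plan's own numbers if strata are crossed, which is the usual reading but is not stated. The size of the power gain depends on unstated event rates and effects, and on site differences being similar across age groups. Confidence in that gain is medium. An AE excess would also be examined through the Mantel-Haenszel test, though that test does not address timing or withdrawal.

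**What to change.** **Correction.** In SAP 9.3.1, change the level to two-sided 0.05; it carries through to 9.3.2. The protocol states no level, so it needs no change for this.

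**Improvement, before unblinding.** In SAP 9.3.1 and 9.3.2, with a note in Section 11, use wording such as:

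*The treatment comparison will use a Cox model with age group as stratum and with treatment and site as main effects (score test, Efron ties, two-sided 0.05 level). Sites with no events contribute no information and will be reported. The log-rank test over all age-by-site combinations will be a sensitivity analysis, with the number of subjects in one-arm strata shown.*

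If the team expects site differences to vary strongly by age group, keep the log-rank as the main test, state that strata are crossed, report the one-arm strata, and make the Cox test the sensitivity analysis.

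**Cost.** A few sentences, a Section 11 note and one extra model; no new data. The statistical price is the loss shown above when age-by-site variation is large, and a slightly higher type I error. The sponsor should confirm that a Section 11 note suffices, because Protocol 7.3.2 names the log-rank test and a protocol amendment would need written IRB submission (Protocol 9.3.3.2.1).

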Time from the first dose to the first AE or to discontinuation from study for any reason will be analyzed using Kaplan-Meier quartile estimates along with 2-sided 95% CIs. Treatment groups will be compared using the log rank test stratified by age group and site. If a subject does not experience any AE or does not discontinue from study, the time to first AE or time to discontinuation will be censored at the date of study completion.

Toxicity grades for laboratory tests will be determined according to the DAIDS AE Grading Table. The maximum postbaseline grade increase from baseline grade will be summarized by treatment group and BID and TID study drug dosing regimen and overall for the Safety Population and PP Safety Population using frequency and percentage of subjects with increase to grade 1, 2, 3, 4, 1 to 4, 2 to 4, and 3 to 4, respectively.

Actual values and changes from baseline for clinical laboratory test results, vital sign measurements, and 12-lead ECG results will be summarized by treatment group and BID and TID study drug dosing regimen at each time point using descriptive statistics (number of subjects, mean, SD, median, minimum, and maximum). Shift tables will be generated for clinical laboratory test results. Physical examination findings will be presented in a data listing.

Narratives will be presented for all deaths, subjects who reported SAEs, subjects withdrawn because of AEs, and grade 3 AEs deemed by the investigator to be possibly, probably, or definitely related to study drug.

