## **4.5. Endpoints**

### **4.5.1 Safety Endpoints**

The primary outcome measure is the evaluation of the safety and tolerability of twice or three times daily oral dosing of TPOXX 600 mg for 28 days through adverse event (AE) findings, clinical laboratory tests, vital sign measurements, electrocardiogram (ECG) tests, and physical examinations. The primary endpoint is the AE rate. Other endpoints include severe AE rate, time to first AE and time to withdrawal for any reason.

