### **9.3. Adverse Events**

The primary objective of this study is to determine the safety and tolerability of TPOXX when administered orally for 28 days in adult subjects. The overall AE rate in the Safety Population and the Per-Protocol Safety Population will be compared between treatment groups using a stratified Mantel-Haenszel test accounting for age (18 to 30 years, 31 to 45 years, 46 to 64 years, and 65 to 80 years). If expected cell counts are less than 5, then Fisher's exact test will be applied. The AE rate is the number of subjects who report at least 1 post-dose AE expressed as a proportion of the number of subjects in the Safety Population and the Per-Protocol Safety Population. An exact unadjusted 95% confidence interval (CI), calculated using the Clopper-Pearson method, will be given for each treatment group. For the difference in AE rates between the treatment groups, a continually corrected exact 95% CI around the difference will be calculated. In addition, the Mantel-Haenszel adjusted odds ratio and 95% Cis from the stratified analysis will be presented.

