### **9.3.2 Time to Withdrawal for Any Reason**

Time to Withdrawal for Any Reason is defined as the duration from start of treatment to study withdrawal for any reason. If the subject does not discontinue from the study, time to withdrawal for any reason will be censored at the date of study completion; this is expected to be the Day 42 (+ 2 days) Follow-up Telephone Call.

Time to Withdrawal for Any Reason (days) = (Date of study withdrawal – Date of first dose) + 1

Time to Withdrawal for Any Reason will be analyzed as described above for the time to first AE.

If a subject does not discontinue or withdraw from the study, the time to discontinuation will be censored at the date of study completion.

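### SAP 9.3.1 sets the log-rank significance level at 0.5, which gives each test of time to first AE and time to withdrawal a 50% false-positive rate

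*Combined protocol and SAP*

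**What the plan says.** SAP Section 9.3.1 plans two things for time to first AE. The first is descriptive: "Kaplan Meier (KM) quartile estimates along with 2 sided 95% CIs". The second is a comparison: "Treatment groups will be compared using the log rank test stratified by age group and clinical investigative site". The next sentence gives the threshold for that comparison: "Statistical significance will be assessed at the 0.5 level".

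Section 9.3.2 does not restate the method. It says: "Time to Withdrawal for Any Reason will be analyzed as described above for the time to first AE". The threshold therefore carries over to the second endpoint.

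SAP Section 4.5.1 names the AE rate as the primary endpoint and adds: "Other endpoints include severe AE rate, time to first AE and time to withdrawal for any reason".

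Nothing elsewhere supplies a different level:

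- Protocol Section 7.3.2 specifies the test ("Treatment groups will be compared using the log rank test stratified by age group and site") with no alpha, and the protocol synopsis does the same.
- SAP Section 9.3, which compares AE rates with a Mantel-Haenszel test, gives no alpha, only 95% intervals (for example "In addition, the Mantel-Haenszel adjusted odds ratio and 95% Cis from the stratified analysis will be presented").
- SAP Section 11, on changes from the protocol, does not touch the point.

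**The concern.** A significance level of 0.5 does not separate signal from chance. When the two arms have the same time-to-event distribution, the log-rank test falls below 0.5 half the time. The level also disagrees with the SAP itself, because every confidence interval in these safety analyses is at 95%.

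Safety and tolerability are the primary objective, and both endpoints are named safety endpoints with a planned between-arm test. Followed literally, the plan would label chance differences as significant in either direction. One direction gives a false tolerability signal against TPOXX, and the other gives an unsupported claim in its favour. If the error is found only after unblinding, a prespecified threshold has to be changed with the results known, and that change has to be explained in the study report.

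**Working it through.** **Inputs**

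| Item | Value | Source |
|---|---|---|
| Stated level, time to first AE | 0.5 | SAP 9.3.1 |
| Level for time to withdrawal | 0.5, by reference | SAP 9.3.2 |
| Confidence level, same paragraph | 95%, two-sided | SAP 9.3.1 |
| Populations for safety analyses | 2 (Safety, PP Safety) | SAP 9 |
| Subjects and allocation | 445, 4:1 (about 356 and 89) | SAP 3 |
| Sites | up to 10 (SAP) or about 12 (protocol) | SAP 4, Pooling of Sites; protocol 4 |
| Age strata | 4 | SAP 4.3 |

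**Step 1: does the stated level follow from the plan's own confidence level?** Alpha = 1 − confidence level = 1 − 0.95 = 0.05, or 0.025 per side. No one-sided or two-sided reading of 95% gives 0.5. Conversely, a level of 0.5 corresponds to a 50% interval. The stated figure is not reproduced.

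**Step 2: what the level means for one test.**

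| | Alpha 0.5 | Alpha 0.05 |
|---|---|---|
| Critical \|z\| (two-sided) | 0.674 | 1.960 |
| Critical chi-square, 1 df | 0.455 | 3.841 |
| False-positive rate per test | 50% | 5% |

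The ratio is 0.5 / 0.05 = 10.

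**Step 3: is the 50% altered by sparse strata or 4:1 allocation?** Four age groups by 10 or 12 sites give up to 40 or about 48 strata. The stratified log-rank test was simulated under no treatment effect with 445 subjects, 4:1 allocation, 42 days of follow-up, and 4, 40 or 48 strata. The documents give no event proportion, so 10% and 40% were assumed. There were 1,500 runs per setting.

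- At 0.5, the simulated size was 48.7% to 50.5%.
- At 0.05, it was 4.7% to 5.4%.

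The Monte Carlo standard error near 50% is √(0.5 × 0.5 / 1,500) = 1.3 percentage points, so the results agree with the nominal levels.

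**Step 4: several tests together.** For k independent tests, the chance of at least one false positive is 1 − (1 − alpha)^k.

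| Tests | Alpha 0.5 | Alpha 0.05 |
|---|---|---|
| 2 (both endpoints, one population) | 1 − 0.5² = 75% | 1 − 0.95² = 9.75% |
| 4 (both endpoints, both populations) | 1 − 0.5⁴ = 93.75% | 1 − 0.95⁴ = 18.5% |

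These tests are positively related, so the joint figures are approximate and probably too high, above all for four tests. Two facts do not need independence. The joint rate cannot fall below the rate for one test, 50%. The expected number of false positives among four null tests is 4 × 0.5 = 2, against 4 × 0.05 = 0.2.

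**The case against.** The strongest reply is that this is a dropped digit that no statistician would apply. The SAP shows other signs of light proofreading: its date still has a placeholder for the day, and Section 9.3 calls an interval continually corrected where the protocol has continuity corrected. That explanation is very probably right. It does not remove the problem, because neither document contains a correct value to fall back on.

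A second reply is that little depends on the threshold. The AE rate is the primary endpoint, and its test carries no stated alpha. The sample size is not based on power. No formal interim analysis is planned, and the halting rules use event counts and causality. The SAP's index of tables lists no time-to-event output, although Section 9.3.1 promises a summary table. All of this is true and limits the consequences. The threshold affects how two non-primary results are labelled and has no bearing on how the trial is run.

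A third reply is that the 95% intervals in Section 9.3.1 belong to Kaplan-Meier quartiles, not to a contrast between arms, so they do not formally fix the log-rank alpha. That is correct as far as it goes. However, SAP Section 9.3 also sets 95% intervals for the between-arm difference in AE rates and for the adjusted odds ratio. The inference to 0.05 is therefore strong, though it remains an inference that the sponsor should confirm.

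Finally, 93.75% is not a realistic estimate. The PP Safety Population is a subset of the Safety Population, and the enrolment goal is for at least 300 of about 356 TPOXX subjects (300/356 = 84%) to reach 92% of dosing. The same test in the two populations will be highly correlated. This point stands, and the conclusion should rest on the 50% per test.

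**Conclusion.** The SAP is wrong as written. The stated level gives a 50% false-positive rate for each log-rank comparison of time to first AE and time to withdrawal, ten times the 5% that matches the plan's 95% intervals. The 50% follows from the definition of the level and needs no assumption beyond an approximately valid test, which the simulation supports. The joint figures of 75% for two tests and 93.75% for four rest on independence and should be read as illustrations.

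The practical reach is limited to two non-primary safety endpoints. The sentence is still an explicit decision rule in the analysis plan, and nothing in either document overrides it, so it must be corrected.

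**What to change.** In SAP Section 9.3.1, change the level for the stratified log-rank test from 0.5 to 0.05 and state that it is two-sided. Section 9.3.2 takes the correction by reference. The sponsor should confirm that two-sided 0.05 was the intended level, since neither document states it anywhere.

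The change is a few characters in one sentence. It has no effect on conduct, data collection or sample size. It should be made and dated before unblinding, so that the threshold remains prespecified.
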